**NRT Sampling Study 3:** Our latest study of NRT sampling is our most real-world test yet: a cluster randomized clinical trial within primary care settings, across South Carolina (22 clinics; N=1245 participants; 2R01 DA021619).(77) Our focus was on the translational potential of medication sampling as a brief, pragmatic intervention that can be offered to a broad spectrum of smokers within clinical context. Outcomes were impressive, and a manuscript is now in review at a top tier journal. More smokers in the NRT group (vs. control) used cessation medication immediately following the clinic visit (55% vs. 10%; AOR = 12.2; 95% CI: 8.3–18.0). That itself is not that impressive, but the fact that medication usage was persistently higher at six months is (25% vs. 14%; AOR = 2.0; 95% CI: 1.5–2.8). NRT sampling increased the rate of quit attempts in the initial month (24% vs. 18%; AOR = 1.7; 95% CI: 1.1–2.6). Most impressively, self-reported point prevalence abstinence rates were significantly higher within the NRT group at 1- (5% vs 2%; AOR = 4.4; 95% CI: 1.8-11.1), 3- (10% vs 5%; AOR = 2.6; 95% CI: 1.6-4.2), and 6-month follow-up (12% vs 8%; AOR = 1.7; 95% CI: 1.1–2.6). Sensitivity analyses revealed comparable results among smokers who were motivated to quit vs. not, demonstrating that NRT sampling was similarly effective for a broad spectrum of smokers. Despite low absolute rates of all quit outcomes (in line with expectation: see Table 1), there was a robust beneficial treatment effect.

One separate but thematically relevant trial, led by [name] (consultant within; co-author [name]), examined more hands on, experiential learning through *in vivo* sampling.(78) We demonstrated that NRT sampling increases adherence for subsequent use, and again demonstrated improvements in attitudinal barriers

that undermine use. Collectively, these NRT sampling studies demonstrate: a) the importance and benefits of randomized yet naturalistic medication sampling studies as a pragmatic means to promote quitting, b) the well-established methods to conduct sampling studies, and c) our collective expertise in doing so.

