## III. Methods

Our three-fold objective is to determine 1) use, 2) consequences, and 3) mechanisms of varenicline sampling. We propose a three-group, randomized clinical trial in which adult smokers, recruited remotely across SC, inclusive of smokers wanting to quit and not, receive a 2-4 week sample of varenicline, combo NRT, or neither, to use as they wish. Remote, serial assessment of carbon monoxide will be used to verify smoking behavior. Uptake and use will be operationally defined as: a) use of medication (incidence, quantity, duration of use), b) conversion to independent use (i.e., obtaining a prescription for further use), and c) adverse events. We anticipate a side effect profile consistent with other trials of varenicline (some insomnia, nausea) but otherwise benign. Cessation-related outcomes include: a) use of additional quit resources (e.g., calls to quitline), b) quit attempts, and c) cessation (7-day point prevalence abstinence, CO verified). Mechanisms include measures of

motivation, confidence, knowledge of and attitudes toward medication, autonomy to quit, expectancies, and cessation fatigue. This is an expanded list from our earlier studies, which allows comparability to NRT sampling but also an opportunity to move forward. Whether and how these non-pharmacologic mechanisms differ for varenicline vs. NRT is an interesting question we can now address, though comparison of mediational models is not our primary focus. An overview of study design is shown in Figure 3.

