For those who elect teleconsent, we will follow IRB-approved procedures as per precedent. Participants who elect to complete the consent process online using doxy.me or REDCap will be consented by IRB-approved study personnel: the PI, study coordinator, or research assistants. All doxy.me signed consent forms will be saved as .pdf files within our study records and all REDCap documents are immediately saved in REDCap. Most of our ongoing studies employ this method, and a growing number of participants prefer this route of consent (currently ~55%). For those opting to receive consent packet through the mail, we will follow our prior procedures described above. Once they have received the consent form in the mail, we will have a scheduled phone call to discuss the consent and study with them. They will have the opportunity to ask any questions at this time, and participants cannot be enrolled without completing the phone discussion step of the consenting process. This phone call was added to our prior mailed consent procedures to ensure that participants have a full understanding of the consent form before enrolling in the study, as they would in person or with online consent.

We have a toll-free phone line to support anyone who calls with questions. Upon return to our office, data are entered into our database, and these individuals comprise the consented sample. However, the sample is reduced further to those with whom we are able to establish first phone contact (Day 0); i.e., the enrolled sample. This enrolled sample is the intent-to-treat sample.

[figure not shown]
Pre-Randomization Verification of Non-Pregnancy: For females age  $\leq 55$ , we impose one additional step to verify pregnancy status. We will mail these participants a commercially available pregnancy test to verify non-pregnancy status. We will then require these participants to confirm in writing via REDCap that they have completed the pregnancy test and have received a negative result. Participants are also informed that they should let us know if they become pregnant during the trial. Medications will not be sent until this verification is in place. These methods are IRB approved (and required) for our proof-of-concept pilot study.

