### *IIId Interventions and procedures*

All smokers in all groups will receive a mailing consisting of standard cessation support materials and specific contact information and benefits of using South Carolina quitline. Quitline benefits will convey the option, for some smokers, to receive free medication. Varenicline participants will receive one-time supply of medication in childproof pill bottle. In our prior sampling studies, we have been largely non-directive of medication use, simply suggesting to participants that they might use it in any number of ways, including not at all. This messaging was consistent with our naturalistic intent, i.e. to allow smokers to self-determine if and how to try the product. For a study of varenicline sampling, we aim to retain naturalistic context but may need to be more directive, including guidance on titration (see dosage comments below). Thus, our messaging will state ~ “*We are offering you a up to a four-week supply of varenicline, which we hope you find helpful. Evidence shows that varenicline is among the best medications to help smokers quit. It is also helpful for smokers who are not yet ready to quit. It is completely up to you if and how you take this. If you decide to try varenicline, start with taking one pill each day for 3 days, followed by a pill in the morning and a pill in the evening thereafter. If you want a stronger dose of medicine to help you quit, you may also go up to two pills in the morning and two pills in the evening after a week. If you ever take a day off and want to re-start, just start this process over again.*” This messaging was drafted and refined by four clinicians and is working well in our pilot study above. This messaging will be conveyed directly during intervention call and also within mailing (with accompanying calendar graphics to facilitate understanding). Both the phone-based and mailing messaging of varenicline sampling will suggest options for continued use beyond the sampling period and will be tailored to individual insurance status. As noted above, study eligibility is restricted to smokers who have access to a medical prescriber who can “convert” interested smokers into more sustained varenicline use. Our mailing will also include a generic letter that smokers can give to their provider stating that they have been pre-screened for and have received varenicline and should be considered for further use upon provider approval. It will be up to the participant to decide if and when to offer this letter to their individual provider. We cannot ensure that this conversion will be seamless, i.e., to occur immediately at the end of sampling period. The extent and timing of conversion is one study outcome.

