
We extensively debated varenicline dosing and sampling duration. Typical practice is to titrate as follows: .5mg QD for days 1-3, .5mg BID for days 4-7, and 1mg BID from day 8 and beyond. On one hand, we want to provide the strongest, most evidence-based dosage possible. If varenicline sampling results in null effect, we do not want this to be due to dosing. On the other hand, providing multiple dosages within a self-paced sampling experience could add unwanted confusion and risk. We are also aware of two large trials that showed similar outcomes of 1mg vs. 2mg dosing, with fewer adverse events in the former.(66, 67) To balance these perspectives, we: a) provide .5mg tablets only, 60 total, b) with instructions to titrate as noted within *italicized instructions* above, c) give instructions to take no more than two in the morning and two in the evening, d) give the participant the ultimate choice to self-pace usage. This choice and pattern of titration becomes an interesting study outcome that aligns with our focus on participant uptake and is wholly consistent with our naturalistic intent. Thus, we view the sampling experience as lasting 2-4 weeks depending on participant choice. For anyone who might ignore the titration schedule and start/restart with 2mg, nausea is the most likely consequence, nothing worse.

Smokers in the NRT group will follow our prior protocol: 4-week supply of both nicotine patch (14mg) and lozenge (4mg), with *comparable instructions for self-determined use as above*. As in our prior trials, we provide both patch and lozenge given different mechanisms of action (slow, cumulative dosing of patch vs. acute delivery for momentary craving with lozenges), and also because of strong evidence to show that superiority of combo NRT over placebo and single NRT products (85-87). We neither explicitly advise nor discourage combined use. Thus, this is an opportunity for smokers to learn about two NRT products, to be used individually or together (participant choice, including none at all). We will caution all participants on signs of receiving too much nicotine (nausea, dizziness) and will monitor adverse events, expected to be rare/mild.

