Outcomes pertaining to uptake, usage and conversion (independent use of varenicline, NRT; Aim 1) are focused *within* each active treatment group individually, though we can compare each of these outcomes *between* medication groups as well, per binary/continuous analyses below. With 360 total participants in varenicline group, a two-sided 95% confidence interval will have a maximum half-width of 0.052 (e.g., 95% CI on an observed rate of 50% would range from 0.448 to 0.552). With 162 participants in NRT group, the maximum half-width for uptake parameters is .077. As the observed proportion deviates from 50% (either higher or lower), the 95% confidence interval will decrease in width, providing more precision on the estimate (e.g., 95% CI on 90% would range from 0.896 to 0.931 with n=324). A confidence interval as wide as +/- 5% is a relatively small width and one we are willing to accept for our estimates on uptake, and conversion. Formal mediation analyses (Aim 3: mechanisms of change, within and between groups) are not planned, but we can test whether the sampling intervention results

in greater change in mechanism variables (\*above) similarly vs. differently for varenicline vs. NRT. All analyses are based on an intent-to-treat approach and are nearly identical to analyses from our current and prior studies. Exploratory analysis will be performed on all variables to determine if transformations are needed. Any significant baseline differences between groups will be included in analyses. All analyses will be run separately for full intent-to-treat sample and those retained per protocol. We are specifically interested in whether sampling effects generalize to those who are and are not motivated to quit, and we will examine this via sensitivity (subgroup) analyses. We are under-powered for tests of treatment interactions.

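### No exposed-participant set is named for adverse events: with every analysis intent-to-treat and use optional, whole-arm rates understate side effects among people who take the medication

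*Combined protocol and SAP*

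**What the plan says.** Section IIIi sets the analysis population in one sentence: "All analyses are based on an intent-to-treat approach and are nearly identical to analyses from our current and prior studies". It adds a second run: "All analyses will be run separately for full intent-to-treat sample and those retained per protocol". Section IIIc fixes who is in the main set: "This enrolled sample is the intent-to-treat sample". Entry to it depends on the first phone contact, not on taking a dose.

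Use is voluntary in both drug arms. Section IIId tells varenicline participants "It is completely up to you if and how you take this", and describes the NRT products as "to be used individually or together (participant choice, including none at all".

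Adverse events are a declared outcome. III. Methods defines uptake and use in three parts, the last two being "b) conversion to independent use (i.e., obtaining a prescription for further use), and c) adverse events". The same section states an expectation: "We anticipate a side effect profile consistent with other trials of varenicline (some insomnia, nausea) but otherwise benign". The Assessments section has each event graded for severity and rated for relatedness to medication. No section states an analysis method or a denominator for adverse events. The only numerical adverse-event criterion, under feasibility in IIIi, is that fewer than 5% of the adverse events from varenicline be serious.

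**The concern.** A participant who never opens the bottle cannot have a drug reaction, yet counts in a whole-arm denominator as someone who had none. Intent-to-treat answers what happens when a sample is offered. It does not give the side-effect rate among people who take the drug, which a clinician or a regulator considering hands-off supply would also want. The background section claims clinical, policy and regulatory significance for this trial, so both figures will be looked for.

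The per-protocol run does not fill the gap. The plan describes it only by retention, and because taking nothing is allowed, a retained participant with no dose has not departed from the protocol and stays in.

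Two readings of the results are at risk. Side effects could look milder than in other varenicline trials partly because some people took nothing. A varenicline–NRT difference in adverse events could also reflect different uptake instead of different tolerability.

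**Working it through.** **Arm sizes.** These come from the abstinence comparison in IIIi: 18% vs 8%, 2:1, 80% power. Two-sided 5% level, pooled variance, no continuity correction, with control/varenicline ratio k = 0.5:

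- pooled proportion = (0.18 + 0.5×0.08)/1.5 = 0.1467
- n(varenicline) = [1.960×√(3×0.1467×0.8533) + 0.8416×√(0.18×0.82 + 0.08×0.92/0.5)]² / 0.10² = 274.9, so 275
- total = 1.5×275 = 412.5, matching the stated 413
- 413/(1 − 0.15) = 485.9, so 486 = 324 + 162, as stated; NRT is also 162.

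The precision paragraph in IIIi states the varenicline half-width of 0.052 for 360 participants and uses 324 only in its 90% example. Either figure is a whole-arm count, so this does not alter the point.

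**Uptake figures in the documents.**

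- Varenicline: feasibility floor of 80% trying it (IIIi); pilot, 83% still using at one month among 23 participants (Preliminary Studies). Ever-use may be higher than 83%.
- NRT: 73% (Study 1), over 85% (Study 2), 55% (Study 3). The Study 3 figure is for those who "used cessation medication immediately following the clinic visit (55% vs. 10"% in control), so it counts any cessation medication, soon after a primary-care visit.

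**Formula.** Let u be the share taking any dose, r the event rate in takers and b the background rate in never-takers.

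- Whole-arm rate = u·r + (1 − u)·b
- Whole-arm excess over background = u·(r − b)

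The drug-related excess is therefore multiplied by u, and the proportion lost is 1 − u.

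- Varenicline: 1 − 0.83 = 17%; 1 − 0.80 = 20%. Never-takers at 80%: 0.20×324 ≈ 65.
- NRT: 1 − 0.85 = 15% up to 1 − 0.55 = 45%. Never-takers: 0.15×162 ≈ 24 up to 0.45×162 ≈ 73.

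**Illustration.** The documents give no adverse-event rate. Assume r = 30%, with b from 0% to 10%:

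| u | whole-arm rate, b = 0% | whole-arm rate, b = 10% |
|---|---|---|
| 0.85 | 25.5% | 27.0% |
| 0.83 | 24.9% | 26.6% |
| 0.80 | 24.0% | 26.0% |
| 0.73 | 21.9% | 24.6% |
| 0.55 | 16.5% | 21.0% |

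A takers-only rate is 30% in every row. At u = 0.80 and n = 324, the Wald 95% interval is 24.0 ± 1.96×√(0.24×0.76/324) = 19.3–28.7% with no background, and 26.0 ± 1.96×√(0.26×0.74/324) = 21.2–30.8% with 10% background.

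**Between drug arms.** With equal tolerability (r = 30%, b = 0) and varenicline uptake of 80%, varenicline shows 24.0%. NRT would show 16.5%, 21.9% or 25.5% at 55%, 73% or 85% uptake. The apparent difference, and its direction, come from uptake alone.

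**Serious-event criterion.** Its denominator is adverse events from varenicline, not participants, so never-takers do not enter it.

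**The case against.** The strongest reply is that the plan never prescribes the analysis at issue. In IIIi, the uptake outcome is use and conversion, and the list of binary outcomes covers quit attempts, cessation, uptake and conversion; adverse events are in neither. Intent-to-treat reaches them only through the word all and through the grouping in III. Methods. This stands: the point is about an omission as much as a choice. But on that reading adverse events have no stated denominator at all, and the same sentence is needed.

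Second, the intervention is the offer of a sample, so whole-arm rates answer the trial's own question. This stands too, and those rates should be kept. A reader might infer that intent-to-treat is wrong for safety here; it is incomplete, not wrong.

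Third, the taker rate could be recovered by dividing by uptake, which the plan will report. That works only when never-takers have no events. With 10% background, 26.0%/0.80 = 32.5%, not 30%. Relatedness ratings sort the numerator and leave the denominator unchanged.

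Fourth, a reader might infer a planned test against other varenicline trials. The documents contain only an expectation about the kind of side effects, with no rate and no test. Individual safety monitoring (real-time flags for suicidal ideation, and diaries) also does not depend on the analysis set.

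**Conclusion.** The point holds as a gap that is cheap to close. Followed as written, per-participant adverse-event rates lose up to about 17–20% of the drug-related excess for varenicline, and possibly more for NRT. If ever-use of varenicline is well above 83%, the loss is smaller. The proportional loss rests only on uptake; the 24–26% illustration also rests on the assumed 30% taker rate and 0–10% background.

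Three stronger inferences are not supported. A 45% loss should not be attached to varenicline, because the 55% behind it comes from an NRT study in primary care with a different measure. It cannot be said that the whole-arm interval would exclude the taker rate: it does at 80% use with zero background, and does not with 10%. The serious-event criterion is not diluted. The abstinence and quit-attempt analyses are not touched.

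**What to change.** In IIIi, after the intent-to-treat sentence, add an exposed safety set: participants who report at least one dose of their assigned medication in the daily diaries or at any follow-up. Report within-arm adverse-event and PHQ-9 event rates in that set beside the intent-to-treat rates, and use the exposed-set rates for any comparison with other varenicline trials. State how many participants have no usable record of use.

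Keep randomised between-arm contrasts on intent-to-treat, and say that they reflect uptake as well as tolerability. The exposed set does not remove that mixture, since takers in each arm are self-selected.

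The cost is one or two sentences and one table. Medication use is already collected in the diaries and follow-ups, so no new data are needed and no clinical procedure changes. The downside is that the exposed set is self-selected and rests on self-report, so it should be labelled descriptive, and its rates will look less favourable.

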If this and future trials suggest efficacy of our sampling approach, this would suggest that physicians can and should give out samples of medications to all smokers, regardless of intent to quit. Our NRT sampling work (below) already supports this view, but whether this applies to varenicline is an entirely different story. It would be a leap to suggest that varenicline sampling would compare to NRT sampling, and this is the very reason this proposal offers innovation. Indeed, if varenicline sampling is found not effective to promote quitting, then this would suggest: a) sampling should be restricted to OTC products, b) sampling should be restricted to products that do not have rigid instructions for administration, and/or c) physician guidance is needed for varenicline use. Whether this trial is positive or negative, outcomes will have important influence on clinical practice.

We are now in prime position for a randomized clinical trial within which our goals are to assess the effects of varenicline sampling across a range of cessation related behaviors: a) use and conversion to sustained medication use beyond sampling, b) quit attempts and cessation (7 day point prevalence abstinence), and to c) evaluate the mechanisms of change: i) confidence,/motivation, ii) autonomy, iii) attitudes towards medication, iv) expectancies. With added comparison group of NRT, we can now make head-to-head comparisons of these two medications on each of these outcomes, even if this comparison is secondary. Sensitivity analyses will examine these outcomes/mechanisms separately for smokers with and without interest in quitting.

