
### *IIIi Power Estimations and Data Analyses*

Power: Our three-fold focus on outcomes includes 1) uptake (usage, conversion), 2) consequences (quit attempts, abstinence), and 3) mechanisms of varenicline and NRT sampling. We power on the most stringent of these to determine sample size: point-prevalence abstinence at six months (Aim 2), and we do so based on primary comparison of varenicline vs. inactive (non-sampling) control; see rationale above. Based on our early work, and under our belief that varenicline sampling will result in marginally better outcomes than NRT (12-15% in our prior studies) we anticipate a quit rate of 18% in varenicline vs. 8% in control, the latter also in line with our prior studies. With 2:1 randomization for this comparison (VRN:control), and with power of 80%, this will require a total sample size of 413 participants across these two groups. We conservatively inflate this by 15% to account for potential attrition, though in past studies this was closer to 12%, thus resulting in 324 varenicline vs. 162 control participants. We secondarily add another, active comparator group of smokers receiving NRT sampling (n=162; 2:1:1 overall randomization), for a **total of 648 participants**. If we were to power on varenicline vs. NRT outcomes, this would require a total sample of 1300 VRN + 650 NRT (+ 160 possible control), and such a study would be infeasible within this mechanism, and likely infeasible within any R01, particularly given the costs of medication. With anticipated 324 varenicline vs. 162 NRT participants, we have 39% power to detect a difference of 18% vs. 12% in abstinence. We have been doing studies this large for some time and have great confidence in recruitment. Over a 48-month recruitment span (see Timeline below), we aim to recruit ~11/month. For our ongoing nationwide trial of e-cigarettes (eventual N=660), we've averaged ~25/month. Considering the recruitment process and minor time delays between consent and formal enrollment, it is difficult to stop at an exact number. Thus, we will enroll between 648-660 participants to abide by those at earlier steps of the process.

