Missing Data & Dropout: The most conservative approach for handling missing data(100) is to substitute them with baseline values, assuming outcomes have all returned to baseline, with no quit attempts made or abstinence achieved. If this assumption is incorrect, it biases the results towards the null by reducing between group differences.(100) We expect few missing data and thus plan for this approach. If missing data >10%, we will calculate results using this conservative method but also using methods in which missing data are imputed as described in the SRNT guidelines, and will assess whether dropout differs by study group (not the case in our prior trials). Abstinence will be reported both with and without (missing samples) CO verification.

Feasibility and Measures of Uptake: Our ongoing proof-of-concept study provides an early sense of study feasibility and thus this is not a main outcome of the trial. Nonetheless, we will deem our approach feasible if: a) at least 80% of varenicline group tries the medication, b) with reasonable duration of use (e.g., median days of use  $\geq 14$  days), c) at least 50% of varenicline group self-titrates to 2mg, d) at least 30% convert to independent use, and e) <5% of adverse events from varenicline are serious.

Binary Outcomes (incidence rate of quit attempts & cessation; % treatment uptake/conversion) will first be examined over the entire study period from baseline to end of follow-up by calculating frequencies/percentages as well as 95% confidence intervals for each medication group. Chi-square tests (or Fisher's exact tests as needed) will compare groups on binary outcomes to determine if effects from sampling group exceed those from control group. Both the control group (primary/powerful comparison) and NRT group (secondary) will serve as referent for varenicline group outcomes. Covariates will be included where necessary based on baseline differences. All tests will be considered significant at the  $\alpha=0.05$  level of significance.

Continuous Outcomes (duration of abstinence, smoking reduction) measured over the entire study period from baseline to the end of follow-up will be evaluated using general linear modeling with a main effect of group to determine group differences. Covariates will be added as necessary to account for baseline group differences.

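### The plan asks whether sampling effects generalise across motivation to quit, but plans only separate subgroup analyses and no estimate of the difference in effect.

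*Combined protocol and SAP*

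**What the plan says.** Wanting to quit (7 or more on a 0-10 scale) is the stratification variable for randomisation (section IIIc, Randomization, Stratification). On its use in the analysis, section IIIi says: "We are specifically interested in whether sampling effects generalize to those who are and are not motivated to quit". It continues: "we will examine this via sensitivity (subgroup) analyses. We are under-powered for tests of treatment interactions". The Summary, Significance, & Scientific Premise section adds: "Sensitivity analyses will examine these outcomes/mechanisms separately for smokers with and without interest in quitting". The Specific Aims call these analyses exploratory.

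For binary outcomes, section IIIi plans percentages with 95% CIs by arm and chi-square or Fisher tests between arms, under one general rule: "All tests will be considered significant at the $\alpha=0.05$ level of significance". It plans no treatment-by-motivation estimate, gives no power for the subgroups, and does not say when effects would count as generalising. Subgroup sizes are not fixed either: the current text sets no quota by motivation, and amendment 16 records that equal recruitment was dropped.

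**The concern.** Whether an effect generalises is a question about the difference between two effects. Analysing each group separately gives two effects, each with its own p-value, but no estimate of that difference and no measure of its uncertainty. Each group holds only part of the sample, so one can reach p<0.05 and the other miss it by chance even when the effect is the same in both. Low power for the interaction does not go away when the sample is split; the same imprecision shows up as conflicting p-values.

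The question matters to the trial's message. The background presents sampling as suitable for smokers whatever their motivation and looks ahead to advice that physicians offer it to all. A report that it worked in only one motivation group would bear directly on that advice.

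**Working it through.** **Inputs (section IIIi).** Assumed rates: "we anticipate a quit rate of 18% in varenicline vs. 8% in control". Allocation is two varenicline participants to each control. Stated sample size: "with power of 80%, this will require a total sample size of 413 participants across these two groups". The allowance for attrition is 15%. Randomised arms: 324 varenicline, 162 control. Sidedness is not stated.

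**1. Reproduce the plan's figure.** Pooled rate p̄ = (0.08 + 2 × 0.18)/3 = 0.1467.

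n(control) = [1.96 √(1.5 p̄(1−p̄)) + 0.8416 √(0.08×0.92 + 0.18×0.82/2)]² / 0.10² = 137.4

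This rounds to 138 control and 275 varenicline, total 413, as stated. A one-sided test (324), a continuity correction (459) or unpooled variance (347) does not give 413, so two-sided 0.05 is used below. Attrition: 413/0.85 = 485.9, that is 486 = 324 + 162, also as stated.

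**2. Power within one group.** Power = Φ[(0.10 − 1.96 s0)/s1], where s0 is the pooled and s1 the unpooled standard error.
- All 486, split 50/50 (162 vs 81 per group): s0 = 0.0481, s1 = 0.0427, power 55.3%.
- 413 evaluable, split 50/50: s0 = 0.0522, s1 = 0.0463, power 48.0%.

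For the undivided comparison the same formula gives 86.5% at 486 and 80.1% at 413.

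**3. Chance of discordant results when the effect is identical.** The groups are independent, so with powers a and b, P(exactly one significant) = a(1−b) + b(1−a).

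| True rates | N | Split | Power per group | Exactly one | Both |
|---|---|---|---|---|---|
| 18% vs 8% | 486 | 50/50 | 55%, 55% | 49.4% | 30.5% |
| 18% vs 8% | 413 | 50/50 | 48%, 48% | 49.9% | 23.0% |
| 18% vs 8% | 486 | 70/30 | 71%, 35% | 56.6% | 24.7% |
| 18% vs 8% | 413 | 70/30 | 63%, 30% | 55.5% | 18.7% |
| 15% vs 8% | 486 | 50/50 | 32%, 32% | 43.9% | 10.5% |
| 15% vs 8% | 413 | 50/50 | 28%, 28% | 40.2% | 7.8% |
| 12% vs 8% | 486 | 50/50 | 14%, 14% | 24.4% | 2.0% |
| 12% vs 8% | 413 | 50/50 | 12%, 12% | 21.9% | 1.6% |

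Exact enumeration and simulation for the first row both give 49.2%. If 15% of the 486 are missing and counted as smoking, the rates become 0.85 × 18% = 15.3% and 0.85 × 8% = 6.8%; power is about 47% per group and discordance about 50%.

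**4. What the contrast would show.** At 486 and 50/50, the standard error of one group's risk difference is √(0.08×0.92/81 + 0.18×0.82/162) = 0.0427. For the difference between the two it is √2 × 0.0427 = 0.0603, a 95% half-width of 1.96 × 0.0603 = 11.8 points. A test of this contrast would wrongly declare a difference in about 5% of trials under identical effects. Its power is about 43% if the effect is 10 points in one group and 0 in the other, which agrees with the plan's caveat on interactions.

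**The case against.** The plan commits to less than a critic might assume, and most of this objection stands.

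- **No decision rule.** A reader might infer that generalisation will be decided by whether each group reaches p<0.05. The documents do not say so. They say the groups will be examined separately, and the only link to significance is the general alpha statement.
- **No exclusion of the interaction.** A reader might also infer that the interaction was ruled out because power is low. The sentence is a caveat. The account of NRT Sampling Study 1 reports a non-significant race-by-treatment interaction and says that trial lacked power for it, so the team does look at such terms. It also went on to read the differing odds ratios as suggestive.
- **Already exploratory.** The label is in the Specific Aims, and no sample-size decision rests on this analysis.
- **The size is conditional.** About half holds for one outcome at the full planned effect. The subgroup analyses also cover mechanisms. If the absolute effect sizes reported for NRT Sampling Study 1 (0.42, 0.46, 0.5, 1.1) held in both groups at 138 vs 69, discordance would be about 30%, 22%, 14% and near zero.
- **The contrast will be imprecise.** Its half-width of 11.8 points exceeds the 10-point planned effect.

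What remains is that no estimate of the difference in effect is planned, and nothing guards against misreading one significant group. The exploratory label supplies neither. A wide interval shows the reader how little the trial can say on this question; two separate p-values hide it.

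**Conclusion.** The point holds as a gap in the planned analysis: a question the plan singles out has no estimate that answers it. The documents do not support the stronger claim that the trial will report an effect confined to one motivation group about half the time, because that needs a decision rule the plan does not contain.

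If separate p-values were used to judge generalisation, identical effects would look different in about 49-50% of trials. That rests on two-sided alpha 0.05, six-month abstinence for varenicline vs control, a true 18% vs 8% in both groups, and an assumed even split. It would be higher with uneven groups (about 56% at 70/30) and lower with smaller effects (about 40-44% at 15% vs 8%, 22-25% at 12% vs 8%). The gap is worth closing before analysis but does not touch the primary comparison.

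**What to change.** Keep the exploratory label and add to section IIIi, for the randomised motivation stratum:

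- stratum-specific effects with 95% CIs;
- the treatment-by-motivation contrast with its 95% CI, on one scale named in advance (for example the risk difference), because whether effects differ can depend on the scale if control quit rates differ by motivation;
- a sentence that significance in one stratum alone will not be read as a difference in effect.

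The cost is SAP wording and one extra model term, with no new data. The interval will be wide, about ±11.8 points at 486 and 50/50, and will usually be inconclusive.
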